PROTOCOL AND STATISTICAL ANALYSIS PLAN

Study Title: Promoting Early Diagnosis of Congenital Hearing Loss with Patient Navigators

Institution/Site:	University of Kentucky
Document (Approval/Update) Date:	03/04/2015
NCT Number:	NCT01917747
IRB Number	46981
Coversheet created:	9/26/2019

Sample Size Calculation and Recruitment: In order to expand the generalizability of this research, we have elected to investigate the efficacy of patient navigation in both Appalachian and non-Appalachian subjects. Non-adherence is a significant problem throughout Kentucky, but more problematic in Appalachia, so we propose to assess the efficacy of a patient navigator in two strata of the same clinical trial (Appalachian and non-Appalachian populations). We have found non-adherence to obtain diagnostic testing after failed infant hearing screen in 27% and 15% of Appalachian and non-Appalachian children, respectively.² We propose that the navigator program will be equally effective on the odds of non-adherence in each of the two strata. Specifically, assuming a common odds ratio of 0.36, we expect the navigator program to decrease nonadherence to 12% and 6% in the Appalachian and non-Appalachian populations, respectively. In order to have 80% power when carrying out a one-tailed Cochran-Mantel Haenszel (CMH) test at the 0.05 significance level, we need 226 subjects, 90 (40%) of whom are from the Appalachian population. We expect that participants may leave the study if they chose to obtain their child's diagnostic testing at another facility outside UK; therefore, we have allowed for a 20% dropout rate. The goal total sample size is 284 participants (114 from the Appalachian population). During 2009-2011, there were 6,739 live births and 258 failed screening tests for a 3.8% failure rate at the University of Kentucky. We will also recruit children who fail newborn hearing screens that are born in other regional hospitals but are referred to our clinic for outpatient testing. Our institution has the highest volume of follow-up infant diagnostic tests after a failed screening test for our region. During 2009- 2011 26,296 live births occurred in hospitals within a 50-mile radius of Lexington with a total of 626 failed newborn hearing screens (2.4% failure rate).

Form B: Medical IRB Research Description

1. Background:

Pediatric hearing loss is the most common neonatal sensory disorder in the United States with an incidence of approximately 1 per 1000 births. The sense of hearing is vital during the early years of life for the development of speech, language, and cognition. Deafness in early childhood can result in lifelong learning delay and disability; however, early identification and intervention can prevent educational and social consequences. Universal newborn hearing screening programs in hospitals have been implemented in most states, including Kentucky, and help in early identification and timely intervention for children born with hearing loss; however, newborn hearing screening is a significant undertaking. This screening does not involve simple blood work, but involves the use of an objective electrophysiological evaluation of the auditory system through the use of an automated auditory brainstem response (AABR) and/or the evoked otoacoustic emissions (OAE) measures. Newborns that fail their hearing screening or high-risk children undergo an audiological diagnostic assessment following discharge and depending on the tests results may have serial assessments with subsequent appropriate intervention. Intervention may include fitting with hearing aids or possibly cochlear implantation. Although high-risk children may undergo periodic audiological assessment, issues such as compliance, socioeconomic factors, and access to care remain major barriers to early identification and subsequent intervention. The consequences of delayed diagnosis and/or failure for appropriate intervention for infants with hearing loss can be significant delay in language, cognitive, and social development. This may lead to adulthood challenges in education and employment. In order to identify newborn hearing loss, hearing screening has become a mandatory component of post-natal care for infants. Mandatory newborn hearing has been recommended by the National Institutes of Health, Joint Committee on Infant Hearing (JCIH), and the American Academy of Pediatrics. The JCIH has established the gold standard of infant screening, follow-up, and intervention and serves as the standard for this study. To summarize the current recommendations, infants are to be screened for hearing loss in the hospital of birth prior to discharge using electrophysiologic tests. If one or both ears fail the testing, an audiologist then performs a complete diagnostic evaluation. A diagnosis of hearing loss should be made before 3 months of age and intervention with amplification should occur prior to 6 months of age. In the event of poor rehabilitation with amplification and continued failed testing, the patient should undergo cochlear implantation by 12 months of age. The benefit of early identification is that timely intervention can improve language and speech acquisition in hearing-impaired children.

Our lab group has assessed the age of diagnosis and age of appropriate intervention in children with hearing loss in Kentucky. We have identified a statistically significant delay in diagnosis and treatment for patients from the Appalachian region of Kentucky. We are also examining the causative factors behind this delay. The lack of education and family support is a common theme in families that fail to follow-up or are delayed in their follow-up. We are proposing a study to examine the effect of a patient navigator to influence patient satisfaction, patient/family behavior and the age of diagnosis of pediatric hearing loss

2. Objectives:

Hypothesis: The assistance of a patient navigator for families with a newborn who failed a newborn hearing-screening test will result in improved patient compliance, patient satisfaction, and age of diagnosis and intervention of pediatric hearing loss.

Specific Aim 1: Examine the effect of a patient navigator to influence the age of diagnosis and intervention for pediatric hearing loss.

Specific Aim 2: Examine the effect of a patient navigator to influence patient satisfaction, knowledge, and compliance with the hearing evaluation and intervention process following newborn hearing screening.

Form B: Medical IRB Research Description

3. Study Design:

For Specific Aim 1, mothers of newborns failing birth hearing screening will be recruited. Participants will be placed into Appalachian and non-Appalachian stratum and then randomized into a patient navigator group or the standard of care group. The navigator group will receive an intervention consisting of educational support from a patient navigator. We will compare the non-adherence rates to obtain the recommended testing within 3 months between groups and strata. The timing of testing will also be assessed and compared between regional strata. At enrollment, we will collect data on maternal socioeconomic status, educational level, and distance from testing center and infant health. Findings will be correlated with adherence to follow-up and timing of services. If the child receives follow up before 3 months and it is determined that child has hearing loss he or she will be approached by a research staff member to participate in the second part of the study (Aim 2) to be randomized and either followed for one year by the patient navigator or to follow standard of care practice.

For Specific Aim 2, mothers of newborns will also be recruited and randomized to navigator vs. no navigator, but this Aim focuses on the diagnosis of hearing loss after the child has had two failed outpatient audiological tests. At the time of hearing loss diagnosis, these participants will be stratified and then randomized similar to Aim 1 into trial arms. Patients will be randomized into 2 groups. Group 1 will have contact with the navigator from the time of hearing loss diagnosis until the first year of life while group 2 will not have the navigator (STANDARD PRACTICE).

4. Study Population and Subject Recruitment Methods and Privacy:

Specific Aim 1: This portion of the study will involve infants born at the University of Kentucky Medical Center, infants born at outside facilities and their families (that are referred to UKMC Audiology Clinic for follow-up testing), and infants and families that are referred to the Commission for Children with Special Health Care Needs (CCSHCN) for follow-up testing. Children that are born at UK undergo newborn hearing screening using a test called ALGO. This test is performed on infants who are older than 34 weeks gestation, have normal external ear, are not on any stimulants, and are in a sleeping or relaxed state approximately 24 hours after birth. This is an automated test that is performed as standard of practice and the results of the test are listed as "PASS" or "REFER." When a child has a "REFER" result then the postpartum nurses or clerk calls the UK ENT clinic (the office of the PI) prior to discharge from the hospital for scheduling a diagnostic hearing test as standard practice. At that point, the PI is an authorized care provider for the patient and that is how the subjects are identified.

The subjects who have a child born at UKMC are approached by a study representative, who physically goes to the patient's hospital room at UKMC to discuss the study. The parents of the child with a failed hearing test will be given a letter (**see attached**) regarding the research project at the time the results are communicated and will be notified that a member of the research team will contact them regarding the study. Once this phone call is made to the PI's office, a member of the research staff will go to the inpatient room in the postpartum ward of UKMC to discuss the study and go over the informed consent/HIPAA documents. If they decline to be in the study then they will tell the study representative at the time that they present the study in the hospital room and they will not be contacted further. They will be verbally reassured that their participation or lack thereof will have no bearing on their or their child's care.

The subjects who are discharged at other facilities will receive telephone contact by the research team once the hospital staff contacts the UK Otolaryngology Clinic for outpatient testing follow up. The CCSHCN staff will also contact the UK research team when a potentially eligible subject has an appointment with them for outpatient follow up testing. The research team will contact potential subjects to confirm their outpatient appointment at their hearing healthcare clinic, providing customer service to patients and providing a secondary understanding of appointment dates and times. At that point, the mothers will be asked if they would like to participate in a research study regarding patient navigation

Form B: Medical IRB Research Description

and be given study details by phone and have opportunity to ask questions. The mothers will be consented by phone (see verbal consent form). If they decline to be in the study then they will tell the study staff member at the time that they present the study by phone and they will not be contacted further. They will be verbally reassured that their participation or lack thereof will have no bearing on their or their child's care.

For either group in Aim 1 there will be no discrimination on age, gender, or ethnicity; however, the parents must be able to speak English or Spanish, as that will be the primary means of communicating with the patient navigator. We expect to enroll approximately 284 subjects in this portion of the study (enrollment should last about 2 years).

Inclusion criteria:

1. Identify parents of children who are born at UKMC in the postpartum ward following mandatory newborn hearing screening, or parents whose children are receiving follow up testing (due to referral after mandatory newborn hearing screening) at UK Audiology or the Commission for Children with Special Health Care Needs
2. Children must be born after 34 weeks gestation
3. Newborns fail hearing screening in one or both ears
4. Parents are willing to have definitive hearing testing performed
5. Parents are willing to be contacted by study coordinators and/or navigator to monitor progress and testing outcomes
6. Parents must be able to speak English or Spanish as the navigator will be speaking one of these languages and this will be the primary means of communication over the phone.

Exclusion criteria:

1. Children who pass their newborn hearing screen
2. Children who are hospitalized past 30 days after birth or who are born prior to 34 weeks gestation
3. Children and parents live outside Kentucky or who will be moving out of Kentucky within the first year of life.
4. Children in the NICU for an extended period of time (they often are delayed in getting their ALGO and subsequent testing)

Specific Aim 2: This segment of the study is evaluating all participants from Aim 1 who fail the follow up outpatient hearing test. This Aim may recruit additional subjects who fail newborn hearing tests from outside hospitals, who are following up for further hearing testing and diagnosed with hearing loss. During study Aim 2, a child is seen once in the Audiology clinic for outpatient follow up hearing testing. Once the child fails the first test, he or she will return for testing with another audiologist to confirm hearing loss. At that point, the research team will be notified that child has met criteria for the second part of the study and parent(s) will be approached with information about the study or will be contacted by phone after the appointment by research staff who will discuss the study and obtain verbal consent and sign consent or provide verbal if they choose to participate.

The parents will be verbally reassured that their participation or lack thereof will have no bearing on their or their child's care. The children who enroll in Aim 2 must meet the same inclusion criteria as Aim 1, except they also must be younger than 6 months old and have a final diagnosis of hearing loss. We expect to enroll 62 subjects, with 31 children from the Aim 1 enrollment and 31 from identified clinic patients who are seen in the Audiology clinic for follow up hearing tests. For this Aim there again will be no discrimination on age, gender, or ethnicity; however, the parents must be able to speak English or Spanish, as that will be the primary means of communicating with the patient navigator.

Patients who previously received navigation in Aim 1 will also be approached by a research staff member after a hearing loss diagnosis is given. These patients will also be consented again for Aim

Form B: Medical IRB Research Description

2 of the study, but they will continue to receive navigation instead of being randomized a second time. This group of patients will also be followed in the study for 12 months.

5. Informed Consent Process:

Aim 1: At the time of the failed ALGO test, the nurse administering the test will give an information letter to the parents of the child who fails the newborn hearing test. As standard practice, the newborn nursery staff calls our clinic to schedule diagnostic hearing testing. That is how a prospective research subject is identified. At that time our research staff will go to the patient room to talk with the parents about the study. A member of the research staff who is authorized to obtain consent will come to inpatient hospital room to discuss the study and obtain consent.

Subjects who have a child who failed the newborn hearing in another facility will be contacted by phone once they have an outpatient hearing screening test (ABR) scheduled. They will have an informed consent by phone through a member of the research staff and will have opportunity to discuss study and ask questions.

Aim 2: At the time of the initial clinic visit for follow up hearing testing, parent(s) of a child who is found to have hearing loss will be approached by research staff who is authorized to obtain informed consent to discuss the study and obtain consent or will be contacted by phone after appointment by research staff who will discuss the study and obtain verbal consent. The parent(s) who signed the consent for the Aim 1 portion of the study and have a child with a final diagnosis of hearing loss through two different ABRs by two different audiologists will be re-consented in the clinic after diagnosis or verbally consented by phone to the current informed consents of the study portion that randomizes to navigation vs. no navigation. Children who were also born in an outside of UK institution, but are followed up with additional outpatient testing with a hearing loss diagnosis are also included.

6. Research Procedures:

Specific Aim 1: The same outcomes will be measured in both groups. Group 1 will be contacted every 2 weeks after discharge from the hospital regarding their child who failed the newborn hearing screen by the patient navigator. This contact will primarily occur through phone calls, but can also occur through email or text messages on a password protected phone if the patient prefers one of these communication methods. Communications between the patient and patient navigator will consist of inquiring on the health and development of the child, addressing questions about hearing, hearing loss, upcoming tests, and intervention services. The navigator will attempt to have these questions answered by clinical staff involved in the patients care and will communicate this to the family. Group 2 will not have navigator contact but will work directly with their hearing healthcare clinic and other referral centers for diagnostic and intervention services (THIS IS THE CURRENT STANDARD OF PRACTICE). Parents in each group of the children born at UKMC, children born at outside facilities (and referred to UKMC Audiology clinic for follow up testing), and children referred to CSHCN for follow up testing will be given a standard brochure that contains basic information about newborn hearing screening and a contact number regarding obtaining further assistance with the diagnostic testing and/or treatment. This is document produced and circulated by the state of Kentucky childhood early hearing detection and intervention agency (SEE APPENDIX 1). At the time of enrollment, parents of the child with the failed hearing screening will fill out a questionnaire which assesses patient satisfaction, knowledge, attitudes, and behaviors, along with some demographic information (**see attached**) from both groups. The subjects who are discharged from outside facilities will have the questionnaire completed by mail, email (through REDCap), or phone with the research staff member. Notes from phone conversations from navigator phone calls will be recorded by the navigator and then recorded on an excel spreadsheet. The data from the questionnaire and the other time points will also be recorded on an excel spreadsheet. At the follow up appointment the research team will also collect data on the outcome of the diagnostic testing. If subjects do not receive their diagnostic follow up within the 3 month time frame

Form B: Medical IRB Research Description

a member of the research team will contact them by phone in order to complete the exit questionnaire and determine if they had diagnostic follow-up at another facility. If the patient cannot be reached by phone the UK research team will work collaboratively with CSHCN to find out (through the EHDI system) if these patients received follow up care in another clinic outside of the study or if they were lost to follow up. This data will be kept in a password-protected file on a password-protected computer and along with the consents will be kept in the locked office of the PI. This data will be kept for a total of 6 years after the conclusion of the study.

Specific Aim 2: The same outcomes will be measured in both groups, but this Aim will focus on the timing of intervention from the hearing screening as an outpatient. The patients randomized to the navigator group will be contacted weekly-biweekly to provide educational and psychosocial support of participants with the same four conversation points from Aim 1. The testing that diagnosed hearing loss will be recorded into the EHDI database. At the time of enrollment, parents of the child with the failed hearing test will also fill out a questionnaire which assesses patient satisfaction, knowledge, attitudes, and behaviors, along with some demographic information (**see attached**) from both groups (navigator and non-navigator). We will have the patients complete the questionnaire at enrollment and 12 months after enrollment. We will also record the age of initial diagnostic test at their hearing healthcare clinic (depending on where the patient received diagnostic testing), age of definitive diagnosis of hearing loss, age of early intervention consultation, age of hearing aid fitting, and (if patient meets criteria for cochlear implantation) age of cochlear implantation. Parent(s) of children in this Aim will also receive another questionnaire, similar to the one they receive at the beginning of Aim 2 that assesses patient satisfaction, knowledge, attitudes and behaviors with follow up demographic information during the one year follow up. Notes from phone conversations from navigator phone calls and data from the questionnaire and at the other time points will be recorded by the navigator and then recorded on an excel spreadsheet. This data also will be kept in a password-protected file on a password-protected computer and along with the consents will be kept in the locked office of the PI. This data also will be kept for a total of 6 years after the conclusion of the study.

7. Resources:

The study does not require any special space. A patient navigator is not a care provider but is an advocate for patients to identify concerns or questions and to help patients navigate through the healthcare system. A phone in a private area of the Audiology clinic will be utilized with an encrypted, password protected computer for data collection and entry. The patient navigator has specialized skill to work with families who have a child with hearing loss and follows Good Clinical Practice when speaking with families. Research staff have experience and training in clinical research and utilize the principles of Good Clinical Practice when screening and enrolling. All have completed appropriate and documented Human Subjects Protection training.

8. Potential Risks and Safety Precautions:

The challenges present in this study relate to the Belmont report issues of respect for persons, beneficence, and justice. The respect for persons becomes an issue in that we are studying children and they are naturally a vulnerable population. A major concern in diagnosing and managing children with hearing loss is that they are lost to follow-up after they leave the hospital. In order to gain access to these children, we need to recruit them while they are in the hospital and approaching them about the study may produce pressure to participate. There is a risk of coercion in this setting. To prevent this coercion, the PI (who could potentially be involved in the patient's care) will not consent the patient or have contact with the patient's family during study Aim 1. The issue of beneficence also comes when dealing with children with hearing loss. If there is miscommunication or misunderstanding of the parents about the information presented or mistrust of the navigator or research team, then this may lead the family further away from the appropriate diagnostic and treatment resources. There are natural safeguards against this as the state of Kentucky monitors failed newborn hearing screening and

Form B: Medical IRB Research Description

independently and families are contacted by the state until they are seen in follow-up. There is also a risk of breach of confidentiality, as we will be contacting this family and interacting with other hearing professionals involved in the care of the child with hearing loss.

When recruiting these patients we will need to be very careful not to be coercive. Parents when they've found out that their child failed a newborn hearing screen may be very susceptible to coercion. The nursery staff will be the first contact, not to discuss the study, but to ask the parents if they'd be willing for the research staff to talk with them about the study. If they say no then they will be ensured that they be provided the standard care as is routine when a child fails a newborn hearing screen. If they agree to participate then the research coordinator will go to the hospital room and meet personally with that family and explain the study. He or she will also become a part of the care team in contacting potential subjects who have children born at outside facilities by confirming appointment times and thereby helping the families in providing appropriate patient service. In asking potential subjects if they would like to participate in the navigator study, the coordinator will not be coercive in his or her approach, but will only give further information if the potential subjects would like more informed knowledge about the study. The coordinator is not a healthcare provider and will not be involved in providing care thus will reduce the pressure of coercion in patients. The navigator will be trained carefully to assist patients, answer their questions, and guide them through the diagnostic and therapeutic process of childhood hearing loss. In order to prevent miscommunication, they will not be allowed to provide medical advice but facilitate their contact with their healthcare providers.

During study Aim 2, child is seen once in the Audiology clinic for outpatient follow up hearing testing. Once the child fails the first test, he or she will return for testing with another audiologist to confirm hearing loss. At that point, a member of the research staff, will be notified that child has met criteria for the second part of the study and parent(s) will be approached or called with information about study and given a consent in-person or will be offered to receive a mailed consent form when called. PI may treat child during the course of the Aim 2 study, but this will be after parent has decided to either participate or decline study.

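### The Study Design ties Aim 2 entry for Aim 1 children to follow-up before 3 months, while the Aim 2 eligibility text admits them up to 6 months; the 3-month condition selects on the Aim 1 adherence outcome

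*Combined protocol and SAP*

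**What the plan says.** All references are to the combined protocol and SAP.

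- **Section 3, Study Design, Aim 1 paragraph.** The Aim 1 comparison is stated as "We will compare the non-adherence rates to obtain the recommended testing within 3 months between groups and strata". The same paragraph then gives the route into Aim 2: "If the child receives follow up before 3 months and it is determined that child has hearing loss", the family is approached and is to be randomised to a year of navigation or to standard care.
- **Section 3, Aim 2 paragraph.** Aim 2 concerns diagnosis "after the child has had two failed outpatient audiological tests", with stratification and randomisation at that point.
- **Section 4, Study Population, Specific Aim 2.** This part of the study is "evaluating all participants from Aim 1 who fail the follow up outpatient hearing test", followed by a confirmatory test with a second audiologist. The Aim 1 criteria apply, except that "they also must be younger than 6 months old and have a final diagnosis of hearing loss". Expected enrolment is 62: 31 from Aim 1 and 31 clinic patients. Children navigated in Aim 1 are consented again but stay in navigation and are not re-randomised.
- **Section 5, Informed Consent Process, Aim 2.** One sentence places the approach at the first follow-up visit. The next refers to a diagnosis from two ABRs by two audiologists and to a study portion that randomises.
- **Sample Size Calculation and Recruitment.** Past experience is "non-adherence to obtain diagnostic testing after failed infant hearing screen in 27% and 15% of Appalachian and non-Appalachian children, respectively". The programme is expected to "decrease nonadherence to 12% and 6% in the Appalachian and non-Appalachian populations".

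**The concern.** Staff applying section 3 would not approach an Aim 1 family whose child was first tested after 3 months. Staff applying section 4 would approach the same family if hearing loss was confirmed before 6 months.

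The section 3 condition is also not a neutral cut-off. Follow-up by 3 months happens after Aim 1 randomisation and is what navigation is meant to change. Entry would therefore depend on an Aim 1 outcome, and if navigation works, more controls than navigator children would fail the condition.

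Two consequences follow. Section 6 says Aim 2 focuses on the timing of intervention and records age at first diagnostic test and at definitive diagnosis; the condition would cut off late first tests among Aim 1 entrants. The clinic-recruited children have no stated 3-month condition, so the two planned halves of Aim 2 would have different eligibility.

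**Working it through.** **1. The entry texts side by side.** Take a child in Aim 1 first tested at 4 months, with hearing loss confirmed before 6 months.
- Section 3: follow-up was not before 3 months, so the stated route into Aim 2 does not apply.
- Section 4: the outpatient test was failed, the diagnosis is final and the child is under 6 months, so the child is eligible.

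The source statement and the criteria in section 4 fit together as one rule. Section 3 conflicts with that rule.

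**2. Inputs from the sample size section.** Non-adherence is 27% (Appalachian) and 15% (non-Appalachian) without the navigator, and 12% and 6% with it. The common odds ratio is 0.36. The test is a one-tailed CMH at 0.05 with 80% power and 226 subjects, 90 of them (40%) Appalachian. The allocation ratio is not stated; I assume 1:1.

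**3. Reproducing the plan's 226.** With n per arm of 45 and 68 in the two strata, the CMH weight is n/2, i.e. 22.5 and 34.
- Weighted difference: 22.5 × 0.15 + 34 × 0.09 = 6.435.
- Null variance, Σ(n/2)·p̄(1 − p̄): 22.5 × 0.195 × 0.805 + 34 × 0.105 × 0.895 = 6.727; square root 2.594.
- Alternative variance, Σ(n/4)·[p₁(1 − p₁) + p₂(1 − p₂)]: 11.25 × 0.3027 + 17 × 0.1839 = 6.532; square root 2.556.
- Power: Φ[(6.435 − 1.645 × 2.594)/2.556] = Φ(0.85) = 80.2%. With the null variance throughout it is 79.8%.

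The required total is 225 or 227, so 226 reproduces. These rates are the ones the plan relies on.

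**4. Share failing a 3-month condition, by Aim 1 arm.**
- Control: 0.4 × 0.27 + 0.6 × 0.15 = 0.198.
- Navigator: 0.4 × 0.12 + 0.6 × 0.06 = 0.084. An odds ratio of exactly 0.36 gives 11.75% and 5.97%, hence 0.083.
- Ratio: 0.198/0.084 ≈ 2.4.
- With 284 enrolled, 142 per arm: about 28 controls and 12 navigator children.

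**5. Effect on the 31 Aim 1 entrants.** Assume hearing loss is equally common in both arms and unrelated to adherence.
- If 31 is the number before the condition is applied: 31 × (0.198 + 0.084)/2 = 4.4 excluded. The difference between Aim 1 arms is 15.5 × (0.198 − 0.084) ≈ 1.8 children.
- If 31 is the number after it is applied: the pool is 31/(1 − 0.141) = 36.1, so about 5 are excluded. The 31 would split 31 × 0.916/(0.916 + 0.802) ≈ 16.5 navigator to 14.5 control.

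**6. Why these are ceilings.** Section 6 expects some families to be lost to follow-up, and a child never tested cannot enter under either text. Let f be the share of non-adherers who are tested late but diagnosed before 6 months. The documents give no value for f. The loss is 4.4 × f: about 1.1 at f = 0.25, 2.2 at f = 0.5 and 4.4 at f = 1. The sample size section also does not say that its 27% and 15% were measured at 3 months.

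**7. Route into the Aim 2 arms.** If every entrant were randomised at Aim 2 entry, as section 3 says, unequal entry by Aim 1 arm would change who is represented but not the balance of the Aim 2 arms. Section 4 instead places all Aim 1 navigator children directly in the Aim 2 navigator group. That group then contains a block, selected through the 3-month condition after navigation, with no counterpart in the non-navigator group.

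**The case against.** The strongest reply is that section 3 is a narrative of study flow and section 4 holds the formal criteria. Section 3 says families meeting the condition will be approached; it does not say that no others will be. On that reading the 3-month phrase is loose wording and section 4 governs. This is fair as far as it goes, but section 3 gives no other Aim 1 route. Section 6 also has families without follow-up by 3 months called for an exit questionnaire, which fits their leaving at that point, though it does not say they are barred from Aim 2. The text still has to be reconciled.

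Several stronger readings are tempting and are not supported:
- *Three incompatible timing rules.* The two section 4 statements can be read as one, so the timing conflict is between two rules.
- *Unequal exclusion by arm as a fact.* It requires a navigator effect. With none, exclusion would be equal.
- *One control child in five lost to Aim 2.* That needs f = 1 and 3-month rates.
- *Selection on the primary outcome.* The documents do not label the outcome primary; adherence is the outcome on which Aim 1 appears to be sized.
- *Bias in Aim 2 from the 3-month condition alone.* It reaches the Aim 2 arms only through the absence of re-randomisation for Aim 1 navigator children.

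It is also right that an under-6-months rule depends partly on the timing of diagnosis, which navigation may change. Moving to it reduces the selection without removing it.

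**Conclusion.** The concern holds as a conflict between section 3 and section 4 over Aim 1 children first tested between 3 and 6 months, joined to a conflict over whether Aim 1 navigator children are randomised again. The section 3 condition selects on 3-month adherence and applies to only one of the two Aim 2 sources.

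Its size is bounded: at most about 19.8% of controls against 8.4% of navigator children, or up to about 4 of 31 entrants, with a between-arm difference of under 2 children. This rests on the plan's rates applying at 3 months, a navigator effect as assumed, 1:1 allocation, a 40/60 stratum split, hearing loss unrelated to adherence, and every non-adherer being tested and diagnosed before 6 months. Relaxing the last assumption lowers the figure. The Aim 1 comparison itself is not affected.

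**What to change.** 1. Delete the 3-month condition from the Aim 2 sentence in section 3. Apply the existing section 4 criterion (final diagnosis, under 6 months of age) to Aim 1 and clinic-recruited children alike. Conform the Aim 2 paragraph of section 3, the opening Aim 2 statement of section 4 and the Aim 2 consent text of section 5 to it.
2. Reconcile section 3 and section 5, which randomise Aim 2 entrants, with section 4, which exempts children navigated in Aim 1.
3. Because the 6-month limit still depends partly on timing, and if Aim 1 navigator children remain un-randomised, report the Aim 2 comparison separately for children randomised at Aim 2 entry and for those carried over from the Aim 1 navigator arm.

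The cost is a few sentences of protocol text, slightly wider eligibility (which helps reach 62) and a little more analysis. The Aim 1 sample size does not change. The separate reporting does leave a smaller randomised comparison: if the 31 Aim 1 entrants split evenly, 62 − 15.5, or about 46 children.
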